#### **13.4.4 Forth Secondary Endpoint Analysis**

To address the Forth Secondary Efficacy Analysis regarding the change from baseline in 17-OHP on the log scale (see [Table 1](#), Analysis 2.4), the analysis and presentation of results will be conducted in exact concordance with the Second Efficacy Analysis of A4 as described in [Section 13.4.1](#) with the only difference being the removal of log A4 as a covariate and the inclusion of the randomization stratification variable (study Week 4 A4 value [0 =  $A4 \leq 4 \times ULN$ ; 1 =  $A4 > 4 \times ULN$ ]) as a fixed factor effect.

#### **13.4.5 Fifth Secondary Endpoint Analysis**

To address the Fifth Secondary Efficacy Analysis regarding the change from baseline in 17-OHP on the absolute scale (see [Table 1](#), Analysis 2.5), the analysis and presentation of results will be conducted in exact concordance with the Third Efficacy Analysis of A4 as described in

[Section 13.4.2](#) with the only difference being the removal of log A4 as a covariate and the inclusion of the randomization stratification variable (study Week 4 A4 value [0 =  $A4 \leq 4 \times ULN$ ; 1 =  $A4 > 4 \times ULN$ ]) as a fixed factor effect.

## 13.5 Exploratory Efficacy Analyses

### 13.5.1 A4 Responder Analysis

The Exploratory Efficacy Analysis 3.1 in [Table 1](#) is the proportion of classic CAH subjects who were randomized into the study who achieve adequate control of serum A4 levels (defined as  $A4 \leq 1x, 1.25x, 1.5x, 1.75x$  and  $2x ULN$ ) 12 weeks from randomization. The efficacy of tildacerfont is evaluated by estimating the odds of meeting a given criterion in the tildacerfont treatment groups to the odds of meeting the criterion in the placebo treatment group. Subjects with missing A4 response data will be considered to non responders.

The proportion of subjects with A4 response will be summarized for each randomized treatment group as the number of subjects at study Weeks 10, 14 and 18 who have achieved a response divided by the total number of subjects randomized to that specific treatment.

#### 13.5.1.1 Statistical Hypotheses

The null hypothesis for a given treatment comparison is that at Week 18 (i.e after the 12 week double-blind, placebo-controlled treatment period), the odds of response to tildacerfont to that of placebo is unity versus the alternative that the relative odds is not unity,

$$H_{0j}: \left\{ \frac{\pi_j}{1 - \pi_j} \right\} \left\{ \frac{1 - \pi_{placebo}}{\pi_{placebo}} \right\} = 1 \quad vs \quad H_{1j}: \left\{ \frac{\pi_j}{1 - \pi_j} \right\} \left\{ \frac{1 - \pi_{placebo}}{\pi_{placebo}} \right\} \neq 1$$

where  $j$  represents tildacerfont dose,  $j = 50, 100$  and  $200$ ,  $\pi_j$  represents the true probability of response for tildacerfont dose  $j$  and similarly for  $\pi_{placebo}$ .

#### 13.5.1.2 Statistical Modeling and Testing

A generalized estimating equations (GEE) model via SAS PROC GENMOD will be used to evaluate A4 response (defined as  $A4 \leq 1x, 1.25x, 1.5x, 1.75x$  and  $2x ULN$ , with a separate

analysis for each ULN cutoff). The model will include response (= 0 or 1) as the dependent variable; treatment group (0 = placebo, 50 = 50 mg QD tildacerfont, 100 = 100 mg QD tildacerfont, and 200 = 200 mg QD tildacerfont), time (=study week 10, 14 and 18), sex (0=male, 1=female), and the interaction of treatment and time as categorical covariates; log baseline A4 and baseline GC dose (in HCe) as continuous covariates. The link function will be logit and distribution will be binomial. Subject IDs are used to identify the repeated measures of visits within subjects with an exchangeable working correlation structure. If the model fails to converge, the following working correlation structures will be tried in order until convergence is reached: unstructured, independent and AR(1). The model will use a binomial distribution with the logit link function and a significance level of 0.05 2-sided.

The odds ratio for response at study Week 18 for each tildacerfont dose level versus placebo group, together with the associated 95% CI and 2-sided p-value will be extracted from the model. The same will also be extracted for the odds ratio of response at study Weeks 10 and 14. SAS code will be of the form,

```
PROC GENMOD DATA=x;
  CLASS SUBJECT TREATMENT VISIT;
  MODEL RESPONSE = TREATMENT VISIT TREATMENT*VISIT / DIST=MULTINOMIAL
    LINK=LOGIT TYPE3 AGGREGATE=TREATMENT;
  REPEATED SUBJECT=PATIENT/TYPE=IND;
  LSMESTIMATE TREATMENT 'OR 50MG V PCBO' -1 1 0 0 / EXP CL ALPHA=0.05;
  LSMESTIMATE TREATMENT 'OR 100MG V PCBO' -1 0 1 0 / EXP CL ALPHA=0.05;
  LSMESTIMATE TREATMENT 'OR 200MG V PCBO' -1 0 0 1 / EXP CL ALPHA=0.05;
RUN;
```

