5.1 Eligibility Criteria

5.1.1 Inclusion Criteria

A subject must meet all of the following criteria to be eligible for this study:

1. Male and female subjects ≥ 18 years old at screening
2. Has a known childhood diagnosis of classic CAH due to 21-hydroxylase deficiency based on genetic mutation in *CYP21A2* and/or documented (at any time) elevated 17-OHP and currently treated with HC, HC acetate, prednisone, prednisolone, methylprednisolone (or a combination of the aforementioned GCs)
3. Has been on a stable, supraphysiologic dose of GC replacement (defined as ≥ 15 mg/day and ≤ 60 mg/day in HCe) for ≥ 1 month before screening
4. Has A4 $>$ ULN at both screening and Week 4 (measured before any AM GC dose) if daily GC dose < 30 mg OR has A4 $> 2.5 \times$ ULN at both screening and Week 4 (measured before any AM GC dose)
5. For subjects with the salt-wasting form of CAH, subject has been on a stable dose of mineralocorticoid replacement for ≥ 1 month before screening
6. Agrees to follow contraception guidelines ([Section 5.2.5](#)). Male subjects must also agree to refrain from donating sperm throughout the treatment period and for 90 days after the last dose of study drug.
7. Is able to understand all study procedures and risks involved and provides written informed consent indicating willingness to comply with all aspects of the protocol.

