9.2 Sample Size Determination

A sample size of n=15 subjects per group will provide at least 80% power to detect a difference of at least 50% in A4 mean percent change from baseline between a given dose level of tildacerfont and placebo, assuming a common SD of 30%.

An assumed dropout rate of 15% during the Treatment Period results in a target of 18 subjects per group and a total sample size of 72 subjects who enter the Treatment Period.

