9.4.4.5 Glucocorticoid Dose Reduction Endpoints

The proportion of subjects with at least a 5 mg/day HCe reduction from baseline in GC dose and A4 \leq ULN at Week 76 will be summarized using an exact score test through logistic regression using the randomization strata and treatment group at Week 76 in the model specification. Missing values for proportion endpoints will not be imputed and will be assumed to be failures. Additional covariates may be specified in the SAP.

Additional GC-related proportions, eg, proportion of subjects at specific dose levels, may be specific in the SAP.

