## **10.5 Multiple Comparisons, Multiplicity**

To control family-wise error rate, statistical hypothesis testing for the primary endpoint will be hierarchically dose ordered, testing first the 200mg dose versus placebo at 0.05 2-sided; then followed by the 100mg dose versus placebo at 0.05 2-sided if the 200mg dose reaches  $p \leq 0.05$ ; and finally, the 50mg dose versus placebo at 0.05 2-sided if the 100mg dose reaches  $p \leq 0.05$ .

Secondary and exploratory endpoints will not be subject to alpha control, rather these endpoints will be interpreted nominally at the 2-sided 5% level.

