### **13.5.2 17-OHP Responder Analysis**

The Exploratory Efficacy Analysis 3.2 in [Table 1](#) is the proportion of classic CAH subjects who were randomized into the study who achieve adequate control of serum 17-OHP levels (defined as  $17\text{-OHP} \leq 1200 \text{ ng/dL}$ ) after 12 weeks of randomized, double-blinded treatment.

These data will be analyzed in the exact same manner as Exploratory Efficacy Analysis 3.1 with the only difference being the exclusion of  $\log A4$  as a covariate and the inclusion of the randomization stratification variable (study Week 4  $A4$  value [ $0 = A4 \leq 4 \times \text{ULN}$ ;  $1 = A4 > 4 \times \text{ULN}$ ]) as a fixed effect in the model.

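### The binary responder GEE has no rule for a cell with zero responders: its only fallback, a different working correlation, cannot cure separation and may never be triggered

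*SAP*

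**What the plan says.** SAP 13.5.1 takes as exploratory analysis 3.1 the proportion of randomised subjects "who achieve adequate control of serum A4 levels", at five cut-offs: 1x, 1.25x, 1.5x, 1.75x and 2x ULN. A missing value counts as non-response.

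SAP 13.5.1.2 fits one binomial-logit GEE per cut-off. Terms are treatment, visit (Weeks 10, 14, 18), their interaction, sex, log baseline A4 and baseline GC dose; tests are at "a significance level of 0.05 2-sided". From each model come the odds ratio, 95% CI and p-value for each dose against placebo at each visit. The working correlation starts as exchangeable. The one contingency is: "If the model fails to converge, the following working correlation structures will be tried in order until convergence is reached", namely unstructured, independent, then AR(1).

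SAP 13.5.2 uses the same model for "adequate control of serum 17-OHP levels" (≤1200 ng/dL), replacing log baseline A4 with the A4 stratum.

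SAP 10.5 sets the weight: "Secondary and exploratory endpoints will not be subject to alpha control".

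On entry, Protocol 5.1.1 criterion 4 requires A4 above "ULN at both screening and Week 4 (measured before any AM GC dose) if daily GC dose" is under 30 mg, or otherwise above 2.5x ULN at both times. Long-term GC dose is held stable in Part A.

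**The concern.** An arm-by-visit cell with no responders has a fitted log odds that runs to minus infinity. Every odds ratio using that cell is then infinite (or zero), and its Wald standard error and p-value carry no information. This is a failure of the mean model. The working correlation describes only the dependence between visits, so exchanging one structure for another leaves the separation in place.

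The fallback also waits for non-convergence. Software can stop iterating and declare convergence with a coefficient of 25 or 30 on the logit scale, in which case the rule is never invoked.

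Placebo at A4 ≤1x ULN is where this is most plausible: entry requires A4 above ULN, GC is held stable, arms are small and missing counts against response. A4 ≤ULN is also the threshold that governs dose escalation in Part B and GC reduction in Part C, so readers will look for it. Without a rule, the sponsor must choose a substitute method after seeing the counts.

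**Working it through.** **Arm size (Protocol 9.2, SAP 7).** 15 per group with 15% dropout: 15 / 0.85 = 17.6, rounded up to 18; 4 × 18 = 72. This reproduces the plan's figure. It was derived for mean percent change in A4 ("assuming a common SD of 30" percent), not for a responder rate.

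**Chance of an empty placebo cell at one visit.** P(0 of n) = (1 − p)^n. The placebo rate p is not in the documents, so a range is assumed. The n = 15 column shows the effect if 3 of 18 are missing and counted as non-responders.

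| Assumed rate p | n = 18 | n = 15 observed |
|---|---|---|
| 2% | 0.98^18 = 70% | 74% |
| 5% | 0.95^18 = 40% | 46% |
| 10% | 0.90^18 = 15% | 21% |
| 15% | 0.85^18 = 5% | 9% |
| 20% | 0.80^18 = 2% | 4% |

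Placebo is the reference for every comparison, so an empty Week 18 placebo cell removes all three dose odds ratios at Week 18.

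**Does the fallback help?** The SAP model was fitted under all four structures to simulated data, 18 per arm, using Python statsmodels. With placebo 0/18 at every visit and 200 mg 8/18 at Week 18, the Week 18 log odds ratio for 200 mg was:

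| Working correlation | Log OR | SE | Reported converged |
|---|---|---|---|
| Exchangeable | 31.4 | 209,000 | yes |
| Unstructured | 32.3 | 65,900 | yes |
| Independent | 26.4 | 1,120 | yes |
| AR(1) | 30.3 | 90,100 | yes |

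The first row gives z = 31.4 / 209,000, about 0.00015, so p is close to 1. On the same counts Fisher's exact test gives 2 × C(18,8) / C(36,8) = 2 × 43,758 / 30,260,340 = 0.003.

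With only the Week 18 placebo cell empty, two simulated datasets gave log odds ratios from −12 to 868, one numerical failure and one undefined SE. One AR(1) fit returned 18.2 with SE 1.84 (z = 9.9), an odds ratio of about 8 × 10^7 with apparently overwhelming significance. The error can therefore go either way.

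**What a penalised fit returns.** For 8/18 v 0/18 without covariates, Firth's estimate equals adding 0.5 to each cell: (8.5 × 18.5) / (10.5 × 0.5) = 30.0. The values at which twice the drop in profile penalised log-likelihood equals 3.84 give a 95% CI of 3.2 to about 4,020. That is wide, but finite and interpretable.

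**Subjects already at target (secondary).** SAP Table 5 puts no baseline condition on response. Below 30 mg/day GC, a subject may enter just above 1x ULN and so already be within 1.25x to 2x. No current 17-OHP level is required. The share affected is not given. As an illustration, assume 20% start at target, 85% of those stay there, and new response is 5% v 30%. Placebo is 0.20 × 0.85 + 0.80 × 0.05 = 21%; active is 0.17 + 0.80 × 0.30 = 41%. A 25-point difference is shown as 20 points, and 0.17 / 0.21 = 81% of placebo responders had nothing to achieve.

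**The case against.** The strongest reply is that little hangs on this. The analyses are exploratory and nominal, the raw proportions by arm and visit are reported whatever the GEE does, and SAP 13.5.1.4 adds a proportional-odds analysis with a rule for collapsing sparse categories. That analysis can give a finite cumulative odds ratio with no placebo subject at ≤1x ULN, provided other categories are populated. All of this stands, and it limits the loss to one set of model estimates. Protocol 9.6 still lists the A4 ≤ULN and 17-OHP ≤1200 ng/dL proportions as secondary endpoints under Type I error control, but SAP 4 says the SAP governs.

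Three stronger readings are tempting and go too far:

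- **A reader might infer that the ≤1x ULN odds ratio will be inestimable.** No placebo normalisation rate appears in either document; at a true rate of 20% the risk is only 2%.
- **A reader might count any empty cell among the 12 arm-by-visit cells.** At assumed placebo rates of 2%, 5% and 10%, with correspondingly rising dose rates, that probability is about 99%, 85% and 46%. But SAP 13.5.1.1 states the hypothesis at Week 18, and with treatment-by-visit terms the 200 mg comparison needs only two cells. With 200 mg rates of 20%, 25% and 30%, the chance that either is empty is 1 − (1 − 0.695)(1 − 0.018) = 70%, and likewise 40% and 15%.
- **A reader might infer that the looser cut-offs are biased.** Randomisation spreads subjects already at target across arms, so the comparison stays valid under the null. The A4 model also adjusts for log baseline A4; the 17-OHP model has no baseline 17-OHP term. Subjects on 30 mg/day or more had to exceed 2.5x ULN at screening and Week 4. Restricting to subjects above the cut-off at baseline is a different estimand with a smaller n.

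**Conclusion.** The gap is real and specific. For the binary A4 and 17-OHP responder models, the written contingency addresses the wrong part of the model and is triggered by the wrong event. Elsewhere the plan does allow for sparse data: the collapse rules in SAP 13.5.1.4 and 13.5.7, and the Protocol 9.4.4.5 GC-reduction endpoint, which "will be summarized using an exact score test through logistic regression".

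The size depends on an unstated placebo rate. At ≤1x ULN the risk of losing all Week 18 odds ratios is substantial at rates of about 5% or below (40% to 70%), moderate at 10% (15%) and small at 15% to 20% (5% to 2%). That separation cannot be cured by the working correlation holds in any software. Convergence being reported anyway was seen in statsmodels on simulated data; SAS may flag it differently, and the SAP does not say what to do if it does.

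No primary or secondary conclusion in the SAP depends on this. The baseline-at-target issue is dilution and labelling, and warrants a supportive display only.

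**What to change.** Add to SAP 13.5.1.2, and by reference to 13.5.2, before unblinding:

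- **Trigger.** Tabulate responders by arm and visit for each cut-off. The rule applies if, at a visit, the placebo cell or the compared dose cell has zero responders or zero non-responders, whether or not the GEE is reported as converged.
- **Method.** Estimate that visit's odds ratio by Firth-penalised logistic regression with the same covariates and a profile-penalised-likelihood 95% CI. Otherwise keep the GEE. State in the table which method produced each estimate.
- **Example code.** The contrasts shown are on treatment alone and so average over visits, which would let an empty placebo cell at any visit spoil the estimate. Write them for each visit.
- **Supportive display.** Beside each all-ITT proportion, show descriptively the proportion among subjects whose baseline exceeds the cut-off (A4 > x times ULN; 17-OHP >1200 ng/dL), with its denominator.

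The cost is a short paragraph, a standard procedure and one extra table column; no new data are needed. The drawback is a method that depends on observed counts, acceptable here because the rule is fixed in advance and the endpoint is exploratory and nominally tested. Penalised intervals from empty cells will be wide and should be read that way.

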### 13.5.1.4 Supportive Analyses: Proportional Odds Analysis

In addition to serial evaluation of A4 response defined as A4  $\leq$  1x, 1.25, 1.5x, 1.75x and 2x ULN, a combined A4 ordinal response will be analyzed, again via a GEE approach. Study Week

18 A4 response will be categorized for each subject as  $\{A=[\leq 1x]; B=[>1x \text{ to } \leq 1.25x]; C=[>1.25x \text{ to } \leq 1.5x]; D=[>1.5 \text{ to } \leq 1.75x]; E=[>1.75 \text{ to } \leq 2.0x]; \text{ and } F=[>2x]\}$  ULN. If there are too few subjects ( $n < 5$ ) in any of the categorizations A to F, the categorized will be collapsed to  $\{\tilde{A}=[\leq 1x]; \tilde{B}=[>1x \text{ to } \leq 1.5x]; \tilde{C}=[>1.5x \text{ to } \leq 2.0x]; \text{ and } \tilde{D}=[>2x]\}$ .

The model will include ordinal A4 response (= A, B, C, D, E, F; or  $\tilde{A}$ ,  $\tilde{B}$ ,  $\tilde{C}$ ,  $\tilde{D}$  if categories are collapsed) as the dependent variable; treatment group (0 = placebo, 50 = 50 mg QD tildacerfont, 100 = 100 mg QD tildacerfont, and 200 = 200 mg QD tildacerfont), time (=study week 10, 14 and 18), sex (0=male, 1=female), and the interaction of treatment and time as categorical covariates; log baseline A4 and baseline GC dose (in HCe) as continuous covariates. The link function will be cumulative logit and distribution will be multinomial. Subject IDs are used to identify the repeated measures of visits within subjects with an exchangeable working correlation structure. If the model fails to converge, the following working correlation structures will be tried in order until convergence is reached: unstructured, independent and AR(1). The significance level will be 0.05 2-sided.

The cumulative odds ratio for response at study Week 18 to each tildacerfont dose level versus placebo group, together with the associated 95% CI and 2-sided p-value will be extracted from the model. The same will also be extracted for the cumulative odds ratio of response at 10 and 14 weeks. SAS code will be of the form,

```
PROC GENMOD DATA=x;
  CLASS SUBJECT TREATMENT VISIT;
  MODEL CATRESPONSE = TREATMENT VISIT TREATMENT*VISIT / DIST=MULTINOMIAL
    LINK=CLOGIT TYPE3 AGGREGATE=TREATMENT;
  REPEATED SUBJECT=PATIENT/TYPE=IND;
  LSMESTIMATE TREATMENT 'CUM OR 50MG V PCBO' -1 1 0 0 / EXP CL ALPHA=0.05;
  LSMESTIMATE TREATMENT 'CUM OR 100MG V PCBO' -1 0 1 0 / EXP CL ALPHA=0.05;
  LSMESTIMATE TREATMENT 'CUM OR 200MG V PCBO' -1 0 0 1 / EXP CL ALPHA=0.05;
  RUN;
```

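### The template SAS code for the exploratory responder analyses targets an unadjusted odds ratio averaged over Weeks 10, 14 and 18, whereas the SAP text asks for adjusted odds ratios at each visit

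*SAP*

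**What the plan says.** SAP 13.5.1.1 fixes the time point: "The null hypothesis for a given treatment comparison is that at Week 18" the odds of response are equal. SAP 13.5.1.2 then names the output in words: "The odds ratio for response at study Week 18 for each tildacerfont dose level versus placebo group", with a 95% CI and two-sided p-value. It adds: "The same will also be extracted for the odds ratio of response at study Weeks 10 and 14". The model in words is a GEE with treatment, time, treatment by time, sex, log baseline A4 and baseline GC dose. The working correlation is exchangeable, with independence only the second fallback if the model does not converge. On distribution: "The link function will be logit and distribution will be binomial".

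The code in the same section is offered as a form, not as final code. Its model line is "MODEL RESPONSE = TREATMENT VISIT TREATMENT*VISIT / DIST=MULTINOMIAL", with no sex, log baseline A4 or GC dose. Its REPEATED statement is "REPEATED SUBJECT=PATIENT/TYPE=IND", although CLASS lists SUBJECT and not PATIENT. Each of its three contrasts has the pattern "LSMESTIMATE TREATMENT 'OR 200MG V PCBO' -1 0 0 1 / EXP CL ALPHA=0.05", with no visit term.

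SAP 13.5.1.4 (the supportive ordinal analysis) asks for "The cumulative odds ratio for response at study Week 18 to each tildacerfont dose level versus placebo group", and again for Weeks 10 and 14. Its code repeats the treatment-only contrasts, the missing covariates, PATIENT and `TYPE=IND`. SAP 13.5.2 prints no code. It says the 17-OHP responder analysis (3.2) follows 3.1 exactly, except that the randomization stratum replaces log A4.

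**The concern.** With a treatment-by-visit interaction in the model, a contrast on the treatment main effect compares least-squares means that give the three visits equal weight. It cannot return a Week 18 odds ratio, nor one for Week 10 or Week 14. For each A4 cut-off the text requires 3 doses × 3 visits = 9 odds ratios; the code prints 3, none tied to a visit. Leaving out the three covariates also changes the quantity estimated, because an unadjusted and an adjusted odds ratio differ even for the same visit.

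A programmer would copy this template for five A4 cut-offs and could carry it to 17-OHP response and the ordinal A4 analysis. SAP Section 4 says the SAP governs over the protocol, but no section says whether text or code governs within the SAP. Until they are reconciled, two different odds ratios can each be defended as the planned one.

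**Working it through.** **Nothing to reproduce.** The documents give no odds ratio, response rate or power for the responder analyses. All response rates below are assumptions.

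**Inputs from the documents.** Visits at study Weeks 10, 14 and 18; missing response counted as non-response (SAP 13.5.1), so each subject contributes three records; a target of 18 per arm (SAP Section 7), used only for one illustration.

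**What the printed contrast targets.** With treatment, visit and their interaction in the model:

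OR from code = exp{(log OR₁₀ + log OR₁₄ + log OR₁₈) / 3}

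This is the geometric mean of the three visit odds ratios.

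**Worked case.** Placebo 10% throughout; active 15%, 22%, 30%.
- OR₁₀ = (0.15/0.85)/(0.10/0.90) = 1.588
- OR₁₄ = (0.22/0.78)/(0.10/0.90) = 2.538
- OR₁₈ = (0.30/0.70)/(0.10/0.90) = 3.857
- Averaged OR = (1.588 × 2.538 × 3.857)^(1/3) = 2.50, which is 0.65 of the Week 18 value.

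**Range over assumed time courses.**

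| Placebo | Active at Weeks 10/14/18 | Week 18 OR | Averaged OR | Averaged ÷ Week 18 |
|---|---|---|---|---|
| 10% | 10/10/30% | 3.86 | 1.57 | 0.41 |
| 5% | 10/20/35% | 10.23 | 4.68 | 0.46 |
| 10% | 15/25/40% | 6.00 | 3.06 | 0.51 |
| 10% | 15/22/30% | 3.86 | 2.50 | 0.65 |
| 10% | 25/35/40% | 6.00 | 4.43 | 0.74 |
| 10% | 30/30/30% | 3.86 | 3.86 | 1.00 |
| 10% | 40/30/20% | 2.25 | 3.73 | 1.66 |

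**Check by model fitting.** Binomial-logit GEEs were fitted in Python to simulated data in which response rises over visits and depends on log baseline A4. Comparisons are 200 mg against placebo.
- One dataset of 200 per arm, no covariates: visit ORs 1.037, 2.746 and 6.302; averaged contrast 2.619. By hand, (1.037 × 2.746 × 6.302)^(1/3) ≈ 2.62, which confirms the formula.
- One dataset of 18 per arm, no covariates (the code's model): Week 18 OR 3.18, averaged 1.47.
- The same 18-per-arm dataset with the three covariates and exchangeable correlation (the text's model): Week 18 OR 5.56 (p = 0.036), averaged 2.45 (p = 0.26).

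**Working correlation.** Without covariates, independence and exchangeable gave identical estimates and robust standard errors, because the data are balanced and the model is saturated. With covariates at 18 per arm, the Week 18 OR was 5.556 (SE 0.837) against 5.559 (SE 0.817).

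**Distribution.** For a 0/1 response, a two-category multinomial is the binomial, so this mismatch does not move the target away from Week 18. In 13.5.1.4 the multinomial distribution and cumulative logit link agree with that section's own text, so `DIST=MULTINOMIAL` in 13.5.1.2 looks carried over.

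**The case against.** The best defence is that the specification is right and the snippet is only a template. The hypothesis, time point, distribution, covariates and correlation are all correctly stated in words. SAP 13.5.1.3 asks for model-based proportions over the three visits. Elsewhere the SAP labels its code as examples, and Appendix D runs on pulse data. A competent programmer would see that three contrasts cannot yield nine odds ratios. The code may not even run as printed (PATIENT absent from CLASS, multinomial with a plain logit link), in which case it would be rewritten from the text. SAS was not available to test this.

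Most of that stands, and it limits the point to a conflict between text and code. It does not remove the point, because the form itself is what is wrong and no rule says the text prevails.

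Several stronger readings are tempting but unsupported:
- *The Week 18 endpoint is wrongly defined.* It is not; the text defines it correctly.
- *Averaged results would be reported as Week 18.* The code's labels name a dose and placebo but no visit.
- *The correlation and distribution mismatches cause the Week 18 miss.* Only the contrast does that. Independence is also on the text's own fallback list.
- *The averaging always dilutes the effect.* It can go either way. Protocol 4.2 reports that response strengthened over 12 weeks in an earlier open-label study, which would favour understatement, but that concerns hormone response at 400 mg QD, not these odds ratios.
- *Analysis 3.2 has the same faulty code.* It has none printed; it inherits the method by reference.

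**Conclusion.** The point holds as a text-code conflict in exploratory analysis 3.1, in the supportive ordinal analysis of 13.5.1.4, and by reference in 3.2. Followed literally, the contrasts and MODEL statement give an unadjusted odds ratio averaged over visits instead of the adjusted odds ratio at each visit. Over the assumed time courses the averaged value runs from 0.41 to 1.66 times the Week 18 odds ratio, and it equals it when the odds ratio is constant over visits. That range rests on assumed rates, and the simulated figures come from single datasets, so neither predicts the trial's result.

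The stakes are limited. SAP 10.5 leaves exploratory endpoints outside alpha control and reads them nominally, and the primary and secondary analyses do not use this code. It should still be corrected, because these odds ratios are to be reported with confidence intervals and p-values.

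**What to change.** In 13.5.1.2:
- Replace the three `LSMESTIMATE TREATMENT` statements with contrasts on `TREATMENT*VISIT` for each dose against placebo at Weeks 10, 14 and 18. For example, with treatments ordered 0, 50, 100, 200 and visit varying fastest, 200 mg against placebo at Week 18 is `0 0 -1 0 0 0 0 0 0 0 0 1`.
- Add sex (also to CLASS), log baseline A4 and baseline GC dose to the MODEL; for 17-OHP use the randomization stratum in place of log baseline A4.
- Use the same subject variable in CLASS and REPEATED.
- For consistency with the text, use `DIST=BINOMIAL` and `TYPE=EXCH`; little numerical effect is expected.

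In 13.5.1.4, keep the multinomial distribution and cumulative logit link. Correct the contrasts, covariates and subject variable. Reconcile the exchangeable structure in the text with `TYPE=IND` in the code, choosing one the procedure supports for multinomial data.

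Add one sentence saying that the text governs where it and illustrative code differ, and run the revised code once on dummy data. The cost is code and wording edits only, with no new data and no design change.
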